2. CORE PROTOCOL

2.1 OBJECTIVES AND HYPOTHESES

2.1.1 Primary Objectives

- 1) To evaluate and characterize the tolerability and safety profile of single agent pembrolizumab (MK-3475) in adult patients with unresectable advanced carcinoma (including NSCLC or MEL).

Hypothesis: Intravenous administration of single agent pembrolizumab (MK-3475) will have acceptable safety and tolerability.

- 2) To evaluate anti-tumor activity of pembrolizumab (MK-3475) in MEL and NSCLC per RECIST 1.1.

Hypothesis: Single agent pembrolizumab (MK-3475) will show a clinically meaningful response rate (RR) or disease-control-rate (DCR) per RECIST 1.1 in ipilimumab-naïve MEL patients, a clinically meaningful RR per RECIST 1.1 in MEL patients previously treated with ipilimumab, a clinically meaningful RR per RECIST 1.1 in MEL patients refractory to ipilimumab, and a clinically meaningful RR per RECIST 1.1 in NSCLC patients that merits further investigation (for details, see Section 3.5, Statistical Analysis Plan).

- 3) To evaluate the extent of tumor response that correlates with the degree of biomarker positivity in the tumors of ipilimumab naïve patients treated with pembrolizumab (MK-3475) with the intent that the cut point for the PD-L1 assay will be explored and refined with tumor samples from ipilimumab-naïve MEL.

Hypothesis: We will be able to define a sub-population of ipilimumab-naïve MEL patients whose tumors express PD-L1. These patients will have a clinically meaningful tumor response compared to ipilimumab naïve MEL patients whose tumors do not express PD-L1.

- 4) To evaluate anti-tumor activity per RECIST 1.1 of pembrolizumab (MK-3475) in unselected MEL refractory to ipilimumab patients and MEL patients refractory to ipilimumab with PD-L1 expressing tumors.

Hypothesis: Single agent pembrolizumab (MK-3475) will show a clinically meaningful response rate (RR) or disease-control-rate (DCR) per RECIST 1.1 in unselected MEL patients refractory to ipilimumab, however single agent pembrolizumab (MK-3475) will show a more clinically meaningful response rate (RR) or disease-control-rate (DCR) per RECIST 1.1 in MEL patients refractory to ipilimumab with PD-L1 expressing tumors.

- 5) To evaluate anti-tumor activity per RECIST 1.1 of pembrolizumab (MK-3475) in patients with NSCLC with at least one prior systemic therapy whose tumors express a high level of PD-L1.

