3.5.3 Analysis Endpoints

3.5.3.1 Efficacy Endpoints

RR and DCR will serve as primary efficacy endpoints only for the ipilimumab-naïve population treated at 10 mg/kg in Part B enrolled through Amendment 4 for internal decision purposes, and the study in this population is considered positive (i.e., demonstration of proof-of-concept in this population) if the outcome in either endpoint is positive. The recently published immune-related response criteria (irRC) as assessed by investigators will be applied as primary measure for assessment of tumor response [18]. RR and DCR will be also assessed based on RECIST 1.1 by blinded central reviewers as supportive analyses. Interim analyses will be based on RR and DCR at Week 12. Confirmation is required for final analysis of RR, but not for the interim analyses. Secondary efficacy endpoints for the above population will include duration of response, progression-free survival (PFS) and overall survival (OS). Response duration will be only determined for confirmed responses and is defined as the time from first documentation of response to first documentation of disease progression or death. PFS will be measured from start of treatment to documentation of definitive disease progression or death due to any cause, whichever occurs first. OS is defined as time from treatment initiation to death due to any cause.

The primary endpoint is RR to further demonstrate the anti-tumor activity of pembrolizumab (MK-3475) in all populations except as noted above. The primary measure for assessment of tumor response is based on RECIST 1.1 by blinded central reviewers and the secondary measure is based on irRC by investigators. DCR, response duration and PFS based on both irRC and RECIST 1.1, and OS will serve as secondary endpoints.

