The randomization of the 250 2L+ patients may be stratified by PD-L1 expression level based on a preliminary cutoff point once available, mainly based on Part C data. Data based on the patients enrolled in the non-randomized portions of Part F (Amendment 06) will be pooled with Part C data, some data from Part A, and possibly data from 1L patients in Part F (Amendment 06), to determine the final cutoff point for patients with strongly positive tumors (the primary population in this cohort) using the same estimation methods as for the melanoma patients. Just like for the melanoma patients, the cutoff point is determined in isolation to the 250 patients enrolled in the randomized portion of Part F (Amendments 07 and 08) to ensure that the subgroup analysis of the patients with strongly positive tumors is blinded to the determination process. Notice that the cutoff point is driven by patients on the Q3W schedule. To properly compare the difference (if any) in cutoff point between the two dose schedules, patients treated at 10 mg/kg Q2W will be divided into two sets with half in the training set and half in the validation set for estimation and validation of a cutoff point specifically for the Q2W schedule.

Enrollment of patients with weakly positive tumors will be capped at 50%. Besides, an interim analysis will be conducted to potentially exclude patients with weakly positive tumors (based on final cutoff point) from further enrollment (see Section 3.5.9 for details). Regardless, the final cutoff point, once determined, won't be changed for the primary analysis purposes to maintain the integrity of the analysis.

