3.5.6 Multiplicity

A Hochberg procedure will be applied to final analysis of RR and DCR for internal decision purposes based on the ipilimumab-naïve patients treated at 10 mg/kg in Part B enrolled through Amendment 4. The overall type I error rate is set at 5% (one-sided),

i.e., the trial is considered to have reached the efficacy objective if the two corresponding p-values for testing the null hypothesis (RR=10% and DCR=30%) are less than 5% OR either one is less than 2.5%. There are two planned interim analyses for administrative purposes. There is no intention to terminate the study early for efficacy, and no multiplicity adjustment is applied to the interim analyses.

The predictive biomarker hypothesis on concordance between tumor volume change and PD-L1 will be formally tested at a type I error rate of 2.5% (one-sided) separately for each part of the study, irrespective of the outcome from efficacy analyses. Once the null hypothesis is rejected, a step-down procedure may be applied to the testing of other biomarker hypotheses prospectively specified before the end of the study. While additional exploratory analyses will be conducted to evaluate alternative predictive biomarkers, there is no multiplicity control of such analyses and no formal conclusion can be made.

The efficacy hypothesis on anti-tumor activity of pembrolizumab (MK-3475) is tested at 5% (one-sided) for Part B ipilimumab-treated (non-randomized), at 10% (one-sided) for Part C, and at 2.5% (one-sided) for all other populations. Between-dose comparisons are all conducted at 20% (two-sided), or equivalent 10% (one-sided) for sample size and power calculation purpose below, except for Part B (10 mg/kg Q3W vs 10 mg/kg Q2W) which is conducted at 5% (two-sided).

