With 40 patients treated at 10 mg/kg Q2W, the study has >90% power to rule out a >30% RR if <8 patients respond (i.e., probability of observing < 8 responses is <10% when true RR is 30%).

Part F NSCLC 2L+ PD-L1 positive (single arm)

With 40 patients treated at 2 mg/kg Q3W, the study has ~90% power to test the null hypothesis of RR =10% at 2.5% type I error rate (one-sided) when the true RR is 30%. A p-value of 2.5% approximately corresponds to an empirical RR of 22.5% (9/40).

Part F NSCLC 2L+ PD-L1 positive (randomized)

Approximately 250 patients will be randomized (3:2) to 10 mg/kg Q3W and 10 mg/kg Q2W. The randomization may be stratified by PD-L1 expression level based on a preliminary cutoff point once available (see Section 3.5.5.4 for details). With 250 patients, the study has approximately 95% power to detect a 15% difference in RR between the two doses at type I error rate of 10% (one-sided) assuming that the RR at 10 mg/kg Q3W is 10%.

Enrollment of patients with weakly positive tumors will be capped at 50% so that at least 75 patients with strongly positive tumors will be treated at 10 mg/kg Q3W. With 75 patients treated at 10 mg/kg Q3W, the study has 85% power to detect a 15% difference in RR between pembrolizumab (MK-3475) and historical control which is conservatively estimated to be 15% (i.e., 30% vs 15%) at type I error rate of 2.5% (one-sided). A p-value of 2.5% approximately corresponds to an empirical RR of 25% (i.e., the lower bound of the 95% CI for an empirical RR at 25% will exclude 15%). With 50 patients at 10 mg/kg Q2W, the study has 68% (or 89%) power to detect a 15% (or 20%) difference in RR between pembrolizumab (MK-3475) and historical control at type I error rate of 2.5% (one-sided). A p-value of 2.5% approximately corresponds to an empirical RR of 28% (i.e., the lower bound of the 95% CI for an empirical RR at 28% will exclude 15%). If 10 mg/kg Q2W has comparable anti-tumor effect to 10 mg/kg Q3W in the population, the two doses will be pooled for a joint analysis as appropriate. Regardless, if the primary analysis in the biomarker strongly positive population is positive a step-down analysis will be performed to assess all biomarker positive patients including patients with weakly positive tumors.

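### The randomised F-2 cohort (second-line-or-later NSCLC) opens its step-down on a primary analysis that the plan never assigns to Q3W, Q2W or their pool

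*Combined protocol and SAP*

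**What the plan says.** Primary objective 5 (Section 2.1.1) concerns "patients with NSCLC with at least one prior systemic therapy whose tumors express a high level of PD-L1" and names no schedule. The endpoint is settled in Section 3.5.3.1: "The primary measure for assessment of tumor response is based on RECIST 1.1 by blinded central reviewers". So is the population: Section 3.5.5.4 refers to patients with "strongly positive tumors (the primary population in this cohort".

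On design, Section 3.5.7 states: "Approximately 250 patients will be randomized (3:2) to 10 mg/kg Q3W and 10 mg/kg Q2W". For strongly positive patients it then gives:

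- Q3W: 75 patients, 30% against a 15% historical control, one-sided 2.5%, 85% power, critical observed rate about 25%.
- Q2W: 50 patients, same control and level, 68% power at 30% and 89% at 35%, critical observed rate about 28%.
- Pool: if the Q2W effect is comparable to Q3W, "the two doses will be pooled for a joint analysis as appropriate". No criterion for comparability, null rate, alpha or power is given.

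The next sentence opens with the word *regardless* and sets the gate: "if the primary analysis in the biomarker strongly positive population is positive a step-down analysis will be performed". The step-down extends the claim to all PD-L1-positive patients.

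Section 3.5.6 sets the efficacy level "at 2.5% (one-sided) for all other populations" that it does not list separately, with no split or order between schedules in this cohort. Section 3.5.5.1 plans 95% confidence intervals by dose/schedule. Section 3.5.8 analyses Part F by line of therapy and dose level. Neither names a primary contrast. Section 3.5 says that no separate SAP will be issued.

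**The concern.** One primary claim has two explicit tests at the full level and a third, optional analysis whose trigger is judged on the same response data. The step-down depends on *the* primary analysis being positive, so the gate must be a single defined test. Here a reader cannot tell before the data whether a given result opens it.

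Two things are at stake. If any positive result may serve as the gate, its error rate exceeds that of one 2.5% test. And the candidates differ greatly in power, so whether the cohort succeeds can turn on which one is called primary afterwards. The study is open-label to sponsor personnel (Section 3.5.1), so that choice could be made with results in view.

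The plan handles this elsewhere. For the randomised Part B Q3W/Q2W cohort, Section 3.5.7 declares a pooled, stratified analysis primary. For the Part B ipilimumab-naïve patients, Section 3.5.6 covers two routes to success with a Hochberg procedure. The F-2 cohort has a formal gate and neither safeguard.

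**Working it through.** **Inputs.** Null 15%, alternatives 30% and 35%, one-sided 2.5%, n = 75 (Q3W) and 50 (Q2W), all from Section 3.5.7. The pool is 75 + 50 = 125; its 2.5% is inferred from the general rule in Section 3.5.6. Sections 1.5 and 2.4.1 randomise 280 (168/112) rather than 250, so half strongly positive gives 84/56 as a second case.

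**1. Reproduce the plan's powers.** Exact binomial test: r is the smallest value with P(X ≥ r | n, 0.15) ≤ 0.025.

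| Test | Cutoff | Exact alpha | Power at 30% | Plan |
|---|---|---|---|---|
| Q3W, n = 75 | 19 (25.3%) | 1.34% | 84.3% | 85% |
| Q2W, n = 50 | 14 (28.0%) | 1.32% | 67.2% | 68% |
| Pool, n = 125 | 28 (22.4%) | 1.78% | 97.7% | none given |

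Q2W power at 35% is 88.4% (plan: 89%). Normal approximations fit worse: for n = 75 they give 90.4% (null variance) or 80.9% (alternative variance). The exact test is therefore taken as the plan's test.

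**2. False opening of the gate, true rate 15% in both schedules.**

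- Q3W or Q2W (independent arms), 75/50: 1.34% + 1.32% − (1.34% × 1.32%) = 2.64%.
- Any of the three, 75/50: sum of b(x; 75, 0.15) × b(y; 50, 0.15) over x ≥ 19, or y ≥ 14, or x + y ≥ 28, which is 3.44%.
- 84/56 (cutoffs 20, 15 and 31 of 140; exact alphas 2.21%, 1.59%, 1.55%): 2.21% + 1.59% − (2.21% × 1.59%) = 3.76% for either schedule, and 4.22% for any of the three.
- Upper bound if each test spent its full 2.5%: 1 − 0.975² = 4.9% for either schedule. Adding a pool with Z = √0.6·Z₁ + √0.4·Z₂ gives 5.8% by simulation.
- Pool counted only if the observed rates lie within 5 or 10 points (assumed criteria), 75/50: 3.34% or 3.44%. Such a trigger barely changes the error.

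**3. Does the choice of primary change the answer?** Same enumeration, equal true rates, 75/50:

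| True rate | Q3W power | Q2W power | Pool power | Pool succeeds, Q3W fails |
|---|---|---|---|---|
| 25% | 51.8% | 36.3% | 77.9% | 27.7% |
| 30% | 84.3% | 67.2% | 97.7% | 13.6% |

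At 84/56 the last column falls to 19.6% and 7.3%.

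An example: 18/75 on Q3W (24%) fails and 10/50 on Q2W (20%) fails, yet together they make 28/125 and the pool succeeds, with observed rates only 4 points apart.

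**The case against.** **Q3W is implied.** The 50% cap on weakly positive tumours is sized to secure 75 strongly positive Q3W patients, Q3W has the larger allocation and the higher power, and Section 3.5.5.4 says the cutoff is driven by Q3W data and puts half the Q2W patients in a training set. This makes Q3W the likeliest intention and Q2W an odd confirmatory gate. It stands as evidence, but it is not a designation: Q2W has its own power statement and critical rate at the same level. If only the validation half of Q2W were tested (25 patients, an assumption), the two rates in step 2 would be 2.1% and 3.2%.

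***Regardless* detaches the gate from pooling.** This is a fair reading of the word's position. On it, the pool is not a route, and at 75/50 the error is 2.64%, practically nominal. Q3W versus Q2W would still be open.

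**Comparability has a test.** Section 3.5.6 says "Between-dose comparisons are all conducted at 20% (two-sided", apart from one Part B comparison. Section 3.5.7 does not link that test to the pooling decision.

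**The stronger reading.** A reader might infer three routes to success, each at a stated 2.5%, and a doubled error rate of 4.9% to 5.8%. The documents do not support that. The 2.5% is explicit only for the two schedules, and those rates assume tests that spend their full level, whereas the plan's powers match conservative exact tests.

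**It is late to specify.** Enrolment is complete (Section 1.5), and Section 3.1.3 already cites the F2 Q3W/Q2W comparison as showing a flat dose-response. A designation made now may be post hoc. This stands, and it shapes the fix.

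**Conclusion.** The concern holds in a limited form. Endpoint, reader, null rate and primary population are all stated; what is missing is the schedule, or pool, that constitutes the primary analysis and opens the step-down. The excess error is modest: 2.6% to 3.4% at 75/50 and 3.8% to 4.2% at 84/56, with 4.9% to 5.8% only as a bound. The lower end of each range applies if the pool cannot open the gate, the upper end if it can.

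The larger consequence is that the conclusion is undetermined in a sizeable share of trials. At 75/50, calling the pool rather than Q3W primary turns failure into success in 28% of trials at a true rate of 25% and in 14% at 30%.

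These figures assume equal true rates in the two schedules, exact binomial tests, the planned numbers of strongly positive patients, and 2.5% for the pool.

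**What to change.** In Section 3.5.7, state that the primary analysis of this cohort, and the only one that opens the step-down, is the response rate per RECIST 1.1 by central review in strongly positive patients on Q3W, tested against 15% at one-sided 2.5%. This designates an analysis and implies no preference between schedules. Exact alpha is 1.3% and power 84% at 75 patients, so the sample size does not change.

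Test Q2W and then the pool only in fixed order after Q3W succeeds, or report them as estimates with 95% confidence intervals, which Section 3.5.5.1 already plans by dose/schedule. Take the conditional pooling out of the gate. Reconcile the 250 patients here with the 280 in Sections 1.5 and 2.4.1.

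If outcome data had been seen when this is specified, list the choice, its timing and its reason in the CSR, as Section 3.5 requires for changes to the statistical methods.

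The cost is a wording change plus that disclosure. The downside is that a positive Q2W or pooled result does not open the step-down when Q3W fails.

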3.5.8 Subgroup Analyses and Effect of Baseline Factors

In assessment of anti-tumor activity in melanoma population, patients will be analyzed by treatment history with ipilimumab and by dose level and dosing interval (Q2W or Q3W). In addition, ipilimumab-naïve patients in Part B will be combined with those in Part D for a sensitivity analysis of treatment difference between the two doses. In assessment of anti-tumor activity in NSCLC populations in Part C and Part F, patients will be analyzed by line of therapy and by dose level.

3.5.9 Interim Analyses

Part B Ipilimumab-Naïve Patients (non-randomized)

The study will have two planned interim analyses for internal decision purpose in ipilimumab-naïve patients treated at 10 mg/kg in Part B enrolled through Amendment 4 (non-randomized). The endpoints in these interim analyses are RR and DCR at week 12. There is no intention to stop the trial for efficacy at the first or second interim analysis. The accrual for Part B is expected to be fast. Should it be slower than expected, one additional interim analysis may be added. The decision rules at the interim analyses serve as guidance and are non-binding. In absence of a control arm, outcomes in this single arm study have to be interpreted with caution, both at interim and final analyses.

The first planned interim analysis will occur when the first 11 patients are evaluable for response assessment at 12 weeks (i.e., have either completed the first tumor re-assessment at week 12 or discontinued the study before week 12). To prevent undue over-enrollment in case the futility bar will be crossed and the study may get terminated early, enrollment of the first 13 MEL patients in Part B will be restricted to ipilimumab-naïve patients.

The futility bar has been set at zero objective response in 11 evaluable patients AND disease control in <5 patients at week 12. This decision criterion has 51% power to rule out the null hypothesis, 89% power to rule out the intermediate effect size and 95% power to rule out the high effect size.

Enrollment will not be stopped for purpose of the first interim futility analysis. Accordingly, approximately 30-38 patients may have been enrolled when the data from that analysis will become available, based on current accrual rate projections. This will include patients without and with prior treatment with ipilimumab.

If the futility bar will be crossed at the first futility analysis (i.e., in case of $\geq 1/11$ responses OR $\geq 5/11$ patients with disease control), enrollment will continue to the

planned sample size for response assessment. If the futility bar will not be crossed at 11 patients, enrollment will be temporarily stopped until all patients who have been already enrolled at the time will have completed their week 12 disease assessment. The number of objective responses or disease control required in this second interim analysis to continue enrollment to the full planned sample size will depend on the number of available patients. In addition, preliminary biomarker data may be taken into account in the decision to continue or stop enrollment.

The second planned interim analysis will be performed when all patients have completed tumor assessment at Week 12 only if the primary objective of the analysis is not met earlier. The primary purpose of this analysis is to provide an early assessment of overall anti-tumor activity, for administrative purpose (e.g., planning of a subsequent study in MEL). A Hochberg procedure with type I error rate of 5% (one-sided) will be applied to assist with the decision. Table 3-6 shows outcomes of interest that are on the borderline of the rejection zone of the null hypothesis, based on various hypothetical sample sizes of evaluable ipilimumab-naïve patients.

Table 3-6

Efficacy Outcome of Interest in Ipilimumab-Naïve Population
at the Second Planned Interim Analysis

Sample size	RR at week 12 (null=5%)		DCR at week 12 (null=30%)	
	Patients with response (%)	Nominal p-Value	Patients with disease control (%)	Nominal p-Value
25	4 (16%)	3.4%	12 (48%)	4.4%
30	5 (17%)	1.6%	14 (47%)	4.0%
35	5 (14%)	2.8%	16 (46%)	3.6%
40	6 (15%)	3.8%	18 (45%)	3.2%

As a comparison to interim analyses, [Table 3-7](#) presents outcome of interest in the ipilimumab-naïve population at the final analysis based on various hypothetical sample sizes. For N varying from 30 to 45, an observed RR of approximately 20-23% OR a DCR of approximately 44-47% is generally required to cross the efficacy bar for a positive study (the bars will be lower when sample size is greater – data not shown in table). If the study objective is not met in the all-comer ipilimumab-naïve population, an exploratory analysis will be conducted in a "biomarker positive" subpopulation determined by the PD-L1 cut-off level. Such an analysis will be only performed if the primary biomarker hypothesis is confirmed, i.e., there will be statistical concordance between PD-L1 expression levels at baseline and maximum total tumor volume reduction (%) produced by pembrolizumab (MK-3475). A Hochberg procedure with type I error rate of 5% (one-sided) will be applied to assist with the analysis.

Table 3-7

Efficacy Outcome of Interest in Ipilimumab-Naïve Population at the Final Analysis

	Study RR (null=10%)		Study DCR (null=30%)	
	Patients with response (%)	Nominal p-Value	Patients with disease control (%)	Nominal p-Value
30	7 (23%)	2.6%	14 (47%)	4.0%
35	8 (23%)	2.0%	16 (46%)	3.6%
40	8 (20%)	4.2%	18 (45%)	3.2%
45	9 (20%)	3.2%	20 (44%)	2.8%

Part F 1L NSCLC PD-L1 positive Patients

For each dose level in Part F 1L, an interim analysis will be conducted after the first 20 patients have had a 3-month follow-up. The accrual to a dose level may be put on hold if ≤ 2 patients have a response. The probability of observing ≤ 2 responses out of 20 patients is $< 10\%$ when the true RR is 25%. After a review of totality of data including tumor volumetric change, disease control rate and safety, the Sponsor will make a decision on whether to resume the accrual.

Part F 2L+ NSCLC PD-L1 positive Patients

There is one planned interim analysis. The primary objective of the interim analysis is to potentially exclude patients with weakly positive tumors (based on final cutoff point) from further enrollment. Based on current projection, the randomized portion may take 11 months to accrue. More interim analyses may be conducted if the accrual rate is slower than expected.

The interim analysis will be conducted after 60 patients in the randomized portion have a minimum follow-up of 12 weeks, which is expected to occur approximately 7 months

after the randomization. The final PD-L1 assay cutoff point for efficacy analyses will be determined before this IA will occur. The target response rate is 20% for interim futility decisions. As guidance, if less than 3 out of 30 patients with weakly positive tumors (i.e., <10%) have a confirmed response no further patients with weakly positive tumors (based on final cutoff point) will be enrolled. The probability of observing less than 3 responses is <4% when the true response rate is 20%. When sample sizes are slightly different, an empirical response rate of <10% will be used as a reference or futility decisions which will also take into account the totality of data. Because the two dose schedules may have different cutoff points, a subgroup analysis by dose schedule will be conducted to determine whether to exclude patients with weakly positive tumors for one schedule or for both (see Section 3.5.5.4 for more details).

Additional Interim Analyses

In addition to the above interim analyses, an interim analysis of Part C may be conducted after all patients have had a 3-month follow-up, interim analyses of Part B ipilimumab-refractory patients and Part D ipilimumab-naive patients (timings to be determined) may be conducted to assist with the dose-selection decision for planning phase 2 studies in melanoma patients, and interim analyses may also be conducted to determine the cutoff points for high PD-L1 patients in melanoma and NSCLC patients (see Section 3.5.5.4).

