3.5.5.4 Predictive Biomarker Analyses

MEL Patients

To address the primary predictive biomarker hypothesis in the MEL population, the following two-step approach will be implemented: 1) estimation of a cutoff point for PD-L1 expression level based on a training set of melanoma patients, and 2) application of the cutoff point to prospectively test the biomarker hypothesis (i.e., formal validation of the cutoff point). The training set consists of patients from the cohort B enrolled through Amendment 04, including 20 ipilimumab-naïve patients at 2 mg Q3, 22 ipilimumab-naïve patients at 10 mg Q3, 41 ipilimumab-naïve patients at 10 mg Q2, 32 ipilimumab-treated patients at 10 mg Q3, and 16 ipilimumab-treated patients at 10 mg Q2. Once the cutoff point is estimated, it will be applied to the analysis of randomized patients in Part B and Part D.

The cutoff point determination process is blinded to the validation analyses to ensure they have the necessary scientific rigor and integrity to confirm a clinical benefit of pembrolizumab (MK-3475) in the "biomarker positive" patients.

Estimation of cutoff point

All patients in the training set are required to have new biopsies such that we expect the yield of tumor samples available for PD-L1 analysis to be very close to the number of patients enrolled. All tumors will be tested retrospectively, with the test operators blinded to all clinical data. Four scoring systems will be evaluated initially: one based on H-score, the other three based on the percentage of tumor cells expressing PD-L1 with minimum intensities of 1+, 2+, and 3+, respectively. The latter two scoring systems (percentage of tumor cells with minimum intensities of 2+ or 3+) may be abandoned if the operators determine that they are too difficult to score.

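### The exploratory PD-L1-positive retest in ipilimumab-naïve melanoma reuses the patients who set the cutoff, so its RR and DCR are biased upward and its 5% error rate is not guaranteed

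*Combined protocol and SAP*

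**What the plan says.** **The retest (3.5.9, text before Table 3-7).** The trigger and label are: "If the study objective is not met in the all-comer ipilimumab-naïve population, an exploratory analysis will be conducted". The subset and the gate are a biomarker-positive "subpopulation determined by the PD-L1 cut-off level. Such an analysis will be only performed if the primary biomarker hypothesis is confirmed". The test is: "A Hochberg procedure with type I error rate of 5% (one-sided) will be applied to assist with the analysis". Section 3.5.6 supplies the gate's level: concordance between tumour volume change and PD-L1 "will be formally tested at a type I error rate of 2.5% (one-sided) separately for each part of the study".

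**The population.** Section 3.5.6 places the RR and DCR test in a cohort defined as "based on the ipilimumab-naïve patients treated at 10 mg/kg in Part B enrolled through Amendment 4". The opening of 3.5.9 uses the same definition.

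**The cutoff (3.5.5.4, melanoma).** "The training set consists of patients from the cohort B enrolled through Amendment 04, including 20 ipilimumab-naïve patients at 2 mg Q3"; the list continues with 22 naïve at 10 mg/kg Q3W, 41 naïve at 10 mg/kg Q2W, 32 treated at 10 mg/kg Q3W and 16 treated at 10 mg/kg Q2W. Up to four scoring systems are compared. The cutoff comes from the Youden index, helped by looking at the ROC curve. The next step is independent: "Once the cutoff point is estimated, it will be applied to the analysis of randomized patients in Part B and Part D".

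**The concern.** A Youden cutoff is placed where it best separates good from poor outcomes in the training data. Some of that separation is chance. RR and DCR measured above the cutoff in the same patients include the chance part, and choosing among several scores adds more. Section 3.5.9 has no sample split, cross-validation or correction for this. The retest also follows a failed test at the same 5% level, with no allowance for the second look.

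At stake is an internal decision. After a miss in all-comers, the team would read an optimistic subgroup rate and a p-value whose stated error rate suggests more assurance than the design gives.

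**Working it through.** **1. The plan's own figures.** Table 3-7 uses p = P(X ≥ x | n, p0) from the binomial distribution. For n = 30, 35, 40, 45 this gives RR 2.58, 2.00, 4.19, 3.20% and DCR 4.01, 3.59, 3.20, 2.83%, all matching. For N = 61, with responders counted within disease control, Hochberg power at RR 25% and DCR 50% is 96.0% (3.5.7 says about 97%). The exact size is 3.9%. The SAP gives no operating characteristics for the retest.

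**2. Overlap.** Training set: 20 + 22 + 41 + 32 + 16 = 131. Naïve at 10 mg/kg: 22 + 41 = 63, and 63/131 = 48%. All 63 are training patients. Table 2-1 gives other counts (41 + 17 = 58 of 58 + 42 + 22 = 122), again 48%.

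**3. Simulation.** Each trial has 131 training patients, 63 of them the retest population, with true RR 10% and DCR 30% at every PD-L1 level. The cutoff is the Youden point on all 131, for one score or the best of four. The gate is Kendall's tau at one-sided 2.5% in the 131. The retest runs if the gate passes and the all-comer test fails; it is an exact-binomial Hochberg test at 5% in the PD-L1-positive patients among the 63. PD-L1 either tracks tumour change within outcome classes without affecting RR or DCR, or is unrelated to everything. The SAP does not give the ROC outcome (response assumed below), the correlation between scores (0.7 assumed), or any limit on the share of patients either side of the cutoff. Results from 15,000 trials each:

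| PD-L1 and outcome | Scores | Minimum share each side | Gate passes | Mean RR above cutoff | Mean DCR above cutoff | Rejects, given run | Run and rejects | Either look rejects |
|---|---|---|---|---|---|---|---|---|
| Tracks change | 1 | none | 99.0% | 16.2% | 34.7% | 5.6% | 5.3% | 9.5% |
| Tracks change | 1 | 20% | 98.8% | 13.1% | 32.5% | 4.6% | 4.4% | 8.2% |
| Tracks change | 4 | 20% | 99.6% | 15.0% | 34.1% | 8.4% | 8.0% | 12.1% |
| Unrelated | 1 | 20% | 2.4% | 13.2% | 32.5% | 17.8% | 0.4% | 4.7% |
| Unrelated | 4 | 20% | 4.0% | 14.8% | 33.8% | 20.6% | 0.8% | 4.7% |

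Variants with 4,000 trials each changed the ROC outcome, the number of scores and the minimum share. With disease control as the ROC outcome, the bias shifts to DCR: 35-40%, with RR about 12-13%. Where PD-L1 tracks change, rejection given run is about 5-6% with one score or just under, and 8-9% with four. Where PD-L1 is unrelated, it is about 9-27%, with the gate passing 2-6% of the time and unconditional error 0.2-1.4%. Those conditional rates rest on few simulated trials and are imprecise.

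**4. Same cutoff, independent patients.** In 88 new patients (Part D's size), mean RR is 10% and mean DCR 30%, and the test rejects in 2.9-3.4% of trials. The error across both looks is still 6.7-7.1% when PD-L1 tracks change. The figure for two independent tests at a full 5% is 1 − 0.95² = 9.75%.

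**5. What Part D can supply.** Section 3.5.7 projects 40-60% high PD-L1. Its pooled 50 to 75 per dose agrees with 0.4 × (80 + 44) = 49.6 and 0.6 × 124 = 74.4, so it applies that range to Part D. Per dose: 0.4 × 44 = 17.6 to 0.6 × 44 = 26.4, or 18-26. Both doses: 35.2 to 52.8, or 35-53. For RR 30% against 10% at one-sided 2.5%, the exact binomial test gives 79% and 94% power at 32 and 48 patients, as 3.5.7 states. At 18 patients (6 or more responses needed) power is 47%; at 26 (7 or more) 70%; at 35 (8 or more) 87%; at 53 (11 or more) 95%.

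**The case against.** The strongest reply is that the plan claims little here. Section 3.5.9 calls the analysis exploratory, uses Hochberg only as an aid, and warns that single-arm results need caution. The whole cohort test is for internal decisions. Independent testing of the locked cutoff is already planned in randomized Part B and Part D patients, with a 10% RR null at one-sided 2.5%. The branch will probably never be used: 3.1.2 reports preliminary response of 47% (RECIST) and 51% (irRC), confirmed plus unconfirmed, in the first 85 melanoma patients. All of this stands, and it limits the weight of the point.

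Three stronger readings are tempting, and the documents do not support them.

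- A reader might infer that the 5% level simply fails, with rejection near one in five. That rate applies only after a gate that rarely opens when PD-L1 is unrelated to outcome. With one score and a restricted cutoff, rejection stays just under 5% even when the gate nearly always opens.
- A reader might infer that 3.5.9 contradicts the train-then-validate rule in 3.5.5.4. That rule governs the validation analyses, and 3.5.9 does not present the retest as validation.
- A reader might infer that the drug could be formally declared active in the subgroup. The positive-study rule in 3.5.3.1 and 3.5.6 concerns the ipilimumab-naïve cohort as a whole.

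The exploratory label does not settle the matter. Section 3.5.6 says that exploratory analyses of alternative biomarkers have no multiplicity control and allow no formal conclusion. Section 3.5.9 instead attaches a numerical error rate to this one.

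**Conclusion.** The point holds as a fault of estimation and labelling in an exploratory, internal-decision analysis. The overlap is complete on the documents' own lists. Upward bias appears in every scenario: RR about 13-17% against 10% when the cutoff is fitted to response (about 12-13% when fitted to disease control), and DCR about 32-40% against 30%. The 68 training patients outside the retest population dilute the bias but do not remove it.

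The 5% level is not guaranteed. It is exceeded unconditionally when PD-L1 tracks tumour change and several scores are compared, and it is kept, by the gate, when PD-L1 is unrelated to outcome. The sizes rest on the assumed ROC outcome, score correlation, rule for choosing the score and limits on the cutoff. The direction of the bias does not.

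**What to change.** In 3.5.9:

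1. Remove the 5% Hochberg test in the Part B patients enrolled through Amendment 4. Report RR and DCR above the cutoff there descriptively, without a p-value, with a bootstrap optimism correction that repeats the choice of both scoring system and cutoff. State the ROC outcome.
2. Base any formal biomarker-positive test on the locked cutoff in the Part D ipilimumab-naïve patients, by dose and pooled, in line with 3.5.5.4 and 3.5.7.
3. Either split alpha between the all-comer and biomarker-positive tests, or state that the error across the two looks is uncontrolled. Moving the test to new patients alone leaves it near 7%.

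This changes SAP wording only and needs no new data. The cost is a smaller independent sample, about 18-26 PD-L1-high patients per dose, with 47-70% power for RR 30% against 10% at one-sided 2.5%. Pooling both doses gives 35-53 patients and 87-95% power, but mixes 2 and 10 mg/kg, whereas the original cohort was treated at 10 mg/kg only. The text should acknowledge that.
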